APPENDIX 1 TFLs Shells

 MC2 Therapeutics
 MC2-01-C6

Listing 16.2.9.2 Local Skin Reactions Assessment
 All Enrolled subjects
 Page X of X

| Country/Site ID/ Subject ID | Age (Years) / Sex/Race/ Ethnicity | Assessment | Visit | Date/ Study Day | Result | Change from Baseline |
|--------------------------------|---|--|---|--|--|----------------------|
| XXX/XX/XXXXX | 14/F/A/NHL | LSR Sum Score | V1 (Day 0) V2/Week2 V3/Week4 ... | YYYY-MM-DD/ XX YYYY-MM-DD/ XX YYYY-MM-DD/ XX | 7 @ 6 Not Done | -1 |
| | | Investigator assessment of erosion/ulceration in lesional area | V1 (Day 0) V2/Week2 V3/Week4 ... | YYYY-MM-DD/ XX YYYY-MM-DD/ XX YYYY-MM-DD/ XX | 2 (Moderate) @ 1 (Mild) Not Done | |
| | | Investigator assessment of vesicles in lesional area | V1 (Day 0) V2/Week2 V3/Week4 ... | YYYY-MM-DD/ XX YYYY-MM-DD/ XX YYYY-MM-DD/ XX | 3 (Severe) @ 2 (Moderate) 2 (Moderate) | |
| | | ... | ... | ... | ... | |
| ... | ... | ... | ... | ... | ... | |

Country: CZE=Czech Republic, HUN=Hungary, DEU=Germany; Sex: F=Female, M=Male;

Race: A=Asian, B=Black or African American, W=White, O=Other; Ethnicity: HL=Hispanic or Latino, NHL=Not Hispanic or Latino.

LSR=Local Skin Reactions.

@ indicates baseline assessment.

^ indicates reported visit is different from the analysis visit after windowing was performed.

Path to the program code, date and time of output/ Datasets used

MC2-01-C6_STATISTICAL ANALYSIS PLAN_Final 3.0_07 September 2020
APPENDIX 1 TFLs Shells

MC2 Therapeutics

MC2-01-C6

Listing 16.2.9.3 Vital Signs

All Enrolled subjects

Page X of X

| Country/Site ID/ Subject ID | Age(Years) / Sex/Race/ Ethnicity | Parameter (Units) | Visit | Date of Assessment/ Study Day | Result | Reference Range | Change from Baseline |
|--------------------------------|--|-------------------------------------|-----------|----------------------------------|--------|-----------------|-------------------------|
| XXX/XX/XXXXXX | 14/F/A/NHL | Systolic Blood Pressure (mm Hg) | V1 (Day0) | YYYY-MM-DD/ XX | XXX @ | XXX - XXX | |
| | | | V2/Week2 | YYYY-MM-DD/ XX | XXX | XXX - XXX | XX |
| | | | V3/Week4 | YYYY-MM-DD/ XX | XXX L | XXX - XXX | XX |
| | | | ... | ... | ... | ... | ... |
| | | Diastolic Blood Pressure (mm Hg) | V1 (Day0) | YYYY-MM-DD/ XX | XX @ | XXX - XXX | |
| | | | V2/Week2 | YYYY-MM-DD/ XX | XX * | XXX - XXX | X |
| | | | V3/Week4 | YYYY-MM-DD/ XX | XX | XXX - XXX | X |
| | | | ... | ... | ... | ... | ... |
| | | | ... | ... | ... | | |
| | | | ... | ... | ... | | |

Country: CZE=Czech Republic, HUN=Hungary, DEU=Germany; Sex: F=Female, M=Male;

Race: A=Asian, B=Black or African American, W=White, O=Other; Ethnicity: HL=Hispanic or Latino, NHL=Not Hispanic or Latino.

L = below lower reference limit. H = above upper reference limit.

@ indicates baseline assessment. * indicates notable value.

^ indicates reported visit is different from the analysis visit after windowing was performed.

Path to the program code, date and time of output/ Datasets used

MC2-01-C6_STATISTICAL ANALYSIS PLAN_Final 3.0_07 September 2020
APPENDIX 1 TFLs Shells

 MC2 Therapeutics
 MC2-01-C6

Listing 16.2.9.4 Electrocardiogram
 All Enrolled subjects
 Page X of X

| Country/Site ID/ Subject ID | Age(Years) / Sex/Race/ Ethnicity | Parameter (Units) | Visit | Date of Visit/ Study Day | Result | Change from Baseline | Findings | Comments/ Technical Quality |
|-----------------------------------|--|----------------------|-----------|-----------------------------|--------------|-------------------------|-------------------|--------------------------------|
| XXX/XX/XXXXXX | 14/F/A/NHL | General Assessment | V1 (Day0) | YYYY-MM-DD/ XX | Normal @ | | | |
| | | | V3/Week4 | YYYY-MM-DD/ XX | Abnormal NCS | | XXXXXXXXXX; XXXXX | XXXXXXXXXXXXXXXXXX |
| | | | V5/Week8 | YYYY-MM-DD/ XX | Abnormal NCS | | | |
| | | | ... | ... | ... | ... | ... | |
| | | RR Interval (msec) | V1 (Day0) | YYYY-MM-DD/ XX | XX @ | | | |
| | | | V3/Week4 | YYYY-MM-DD/ XX | XX * | XX | | |
| | | | V5/Week8 | YYYY-MM-DD/ XX | XX | XX | | |
| | | | ... | ... | ... | ... | ... | |
| | | | ... | ... | ... | ... | | |
| | | | ... | ... | ... | ... | | |

Country: CZE=Czech Republic, HUN=Hungary, DEU=Germany; Sex: F=Female, M=Male;

Race: A=Asian, B=Black or African American, W=White, O=Other; Ethnicity: HL=Hispanic or Latino, NHL=Not Hispanic or Latino.

L = below lower reference limit. H = above upper reference limit. CS = Clinically Significant. NCS = Not Clinically Significant.

@ indicates baseline assessment. * indicates notable value.

^ indicates reported visit is different from the analysis visit after windowing was performed.

Path to the program code, date and time of output/ Datasets used

**MC2-01-C6_STATISTICAL ANALYSIS PLAN_Final 3.0_07 September 2020**
APPENDIX 1 TFLs ShellsMC2 Therapeutics
MC2-01-C6**Listing 16.2.9.5 Physical Parameters**
All Enrolled subjects
Page X of X

| Country/Site ID/ Subject ID | Age (Years) / Sex/Race/ Ethnicity | Parameter (Units) | Visit | Date of Visit/ Study Day | Result | Change from Baseline |
|--------------------------------|---|-------------------|--|---|----------------------------------|----------------------|
| XXX/XX/XXXXX | 14/F/A/NHL | Weight (kg) | V1 (Day0) V2/Week2 V3/Week4 ... | YYYY-MM-DD/ XX YYYY-MM-DD/ XX YYYY-MM-DD/ XX ... | [contact] XX.X ... | X X |
| | | Height (cm) | V1 (Day0) V2/Week2 V3/Week4 ... | YYYY-MM-DD/ XX YYYY-MM-DD/ XX YYYY-MM-DD/ XX ... | [contact] XXX.X ... | X X |
| | | BMI (kg/m2) | ... | ... | ... | ... |
| | | | ... | | | |

Country: CZE=Czech Republic, HUN=Hungary, DEU=Germany; Sex: F=Female, M=Male;

Race: A=Asian, B=Black or African American, W=White, O=Other; Ethnicity: HL=Hispanic or Latino, NHL=Not Hispanic or Latino.

^ indicates reported visit is different from the analysis visit after windowing was performed.

Path to the program code, date and time of output/ Datasets used

**MC2-01-C6_STATISTICAL ANALYSIS PLAN_Final 3.0_07 September 2020**
APPENDIX 1 TFLs ShellsMC2 Therapeutics
MC2-01-C6**Listing 16.2.9.6 Physical Examination**
All Enrolled subjects
Page X of X

| Country/Site ID/ Subject ID | Age(Years)/ Sex/Race/ Ethnicity | Examination | Visit | Date of Visit/ Study Day | Result |
|--------------------------------|---------------------------------------|--|---|---|---|
| XXX/XX/XXXXX | 14/F/A/NHL | Abbreviated Physical Examination | Scr V1 V1 (Day 0) V3/Week4 V5/Week8 ... | YYYY-MM-DD/ XX YYYY-MM-DD/ XX YYYY-MM-DD/ XX ... | Normal Abnormal NCS Normal Not Done ... |
| | | Complete Dermatological Examination | Scr V1 V1 (Day 0) V3/Week4 V5/Week8 ... | YYYY-MM-DD/ XX YYYY-MM-DD/ XX YYYY-MM-DD/ XX ... | Abnormal CS Normal Normal Normal ... |
| ... | ... | ... | ... | ... | ... |

Country: CZE=Czech Republic, HUN=Hungary, DEU=Germany; Sex: F=Female, M=Male;

Race: A=Asian, B=Black or African American, W=White, O=Other; Ethnicity: HL=Hispanic or Latino, NHL=Not Hispanic or Latino.

CS = Clinically Significant. NCS = Not Clinically Significant.

^ indicates reported visit is different from the analysis visit after windowing was performed.

Path to the program code, date and time of output/ Datasets used

MC2-01-C6_STATISTICAL ANALYSIS PLAN_Final 3.0_07 September 2020
APPENDIX 1 TFLs Shells

MC2 Therapeutics
MC2-01-C6

Listing 16.2.9.7 Physician Global Assessment of Psoriasis Severity

All Enrolled subjects

Page X of X

| Country/Site ID/ Subject ID | Age(Years) / Sex/Race/ Ethnicity | Visit | Date/ Study Day | Result | Change from Baseline | Treatment Success |
|--------------------------------|--|------------|-----------------|----------------|----------------------|-------------------|
| XXX/XX/XXXXX | 14/F/A/NHL | Scr V1 | YYYY-MM-DD/ XX | 3 - Moderate | | |
| | | Scr V2 | YYYY-MM-DD/ XX | 3 - Moderate | | |
| | | V1 (Day 0) | YYYY-MM-DD/ XX | 3 - Moderate @ | | |
| | | V2/Week2 | YYYY-MM-DD/ XX | 2 - Mild | -1 | |
| | | V3/Week4 | | Not Done | | |
| | | ... | | | | |
| XXX/XX/XXXXX | 15/M/W/HL | Scr V1 | YYYY-MM-DD/ XX | 3 - Moderate | | |
| | | Scr V2 | YYYY-MM-DD/ XX | 3 - Moderate @ | | |
| | | V1 (Day 0) | | Not Done | | |
| | | V3/Week4 | YYYY-MM-DD/ XX | 0 - Clear | -3 | Yes |
| | | V5/Week | YYYY-MM-DD/ XX | 0 - Clear | -3 | Yes |
| | | ... | | | | |

Country: CZE=Czech Republic, HUN=Hungary, DEU=Germany; Sex: F=Female, M=Male;

Race: A=Asian, B=Black or African American, W=White, O=Other; Ethnicity: HL=Hispanic or Latino, NHL=Not Hispanic or Latino.

L = below lower reference limit. H = above upper reference limit.

@ indicates baseline assessment.

^ indicates reported visit is different from the analysis visit after windowing was performed.

Treatment success is defined as at least 2-point decrease from Baseline in the PGA on the trunk, limbs, and scalp.

Path to the program code, date and time of output/ Datasets used

MC2-01-C6_STATISTICAL ANALYSIS PLAN_Final 3.0_07 September 2020
APPENDIX 1 TFLs Shells

 MC2 Therapeutics
 MC2-01-C6

Listing 16.2.9.8 Body Surface Area Involvement
 All Enrolled subjects
 Page X of X

| Country/Site ID/ Subject ID | Age(Years)/ Sex/Race/ Ethnicity | Parameter (Units) | Visit | Date/ Study Day | Result | Change from Baseline |
|--------------------------------|---------------------------------------|---|---|---|--|----------------------|
| XXX/XX/XXXXX | 14/F/A/NHL | Scalp BSA psoriatic involvement (%) | Scr V1 Scr V2 V1 (Day 0) V3/Week4 V5/Week8 ... | YYYY-MM-DD/ XX YYYY-MM-DD/ XX YYYY-MM-DD/ XX YYYY-MM-DD/ XX YYYY-MM-DD/ XX ... | XX.X XX.X [contact] XX.X Not Done | XX.X |
| | | Neck, Trunk and/or Limbs BSA psoriatic involvement (%) | Scr V1 Scr V2 V1 (Day 0) V3/Week4 V5/Week8 ... | YYYY-MM-DD/ XX YYYY-MM-DD/ XX YYYY-MM-DD/ XX YYYY-MM-DD/ XX YYYY-MM-DD/ XX ... | XX.X XX.X @ Not Done XX.X XX.X ... | XX.X |
| | | | | | | XX.X |
| ... | | | | ... | ... | ... |
| ... | | | | ... | ... | ... |

Country: CZE=Czech Republic, HUN=Hungary, DEU=Germany; Sex: F=Female, M=Male;

Race: A=Asian, B=Black or African American, W=White, O=Other; Ethnicity: HL=Hispanic or Latino, NHL=Not Hispanic or Latino.

BSA=Body Surface Area.

@ indicates baseline assessment.

^ indicates reported visit is different from the analysis visit after windowing was performed.

Path to the program code, date and time of output/ Datasets used

MC2-01-C6_STATISTICAL ANALYSIS PLAN_Final 3.0_07 September 2020
APPENDIX 1 TFLs Shells

 MC2 Therapeutics
 MC2-01-C6

Listing 16.2.9.9 Psoriasis Treatment Convenience Scale
 All Enrolled subjects
 Page X of X

| Country/Site ID/ Subject ID | Age (Years) / Sex/Race/ Ethnicity | Visit | Date/ Study Day | Parameter/Question | Score/Answer |
|--------------------------------|---|-----------|-----------------|--|---------------------------------|
| XXX/XX/XXXXX | 14/F/A/NHL | V2/Week 2 | YYYY-MM-DD/ XX | PTCS Total Score 1. How easy was the treatment to apply to the skin? 2. How greasy was the treatment when applying it to the skin? 3. How moisturized did your skin feel after applying the treatment? ... | XX X X Not Done ... |
| | | V3/Week4 | YYYY-MM-DD/ XX | PTCS Total Score 1. How easy was the treatment to apply to the skin? 2. How greasy was the treatment when applying it to the skin? 3. How moisturized did your skin feel after applying the treatment? ... | XX X X Not Done ... |
| | | V5/Week8 | YYYY-MM-DD/ XX | PTCS Total Score 1. How easy was the treatment to apply to the skin? 2. How greasy was the treatment when applying it to the skin? 3. How moisturized did your skin feel after applying the treatment? ... | XX X X Not Done ... |
| | | ... | ... | ... | ... |

Country: CZE=Czech Republic, HUN=Hungary, DEU=Germany; Sex: F=Female, M=Male;

Race: A=Asian, B=Black or African American, W=White, O=Other; Ethnicity: HL=Hispanic or Latino, NHL=Not Hispanic or Latino.

PTCS=Psoriasis Treatment Convenience Scale. Question 1: From 1 = Very difficult to 10 = Very easy. Question 2: From 1 = Very greasy to 10 = Not greasy.

Question 3: From 1 = Not moisturized to 10 = Very moisturized. Question 4: From 1 = Very greasy to 10 = Not greasy. Question 5: From 1 = Very disturbing to 10 = Not disturbing. Question 6: From 1 = Not satisfied to 10 = Very satisfied.

PTCS total score is the sum of the scores on questions 1 to 5.

^ indicates reported visit is different from the analysis visit after windowing was performed.

Path to the program code, date and time of output/ Datasets used

MC2-01-C6_STATISTICAL ANALYSIS PLAN_Final 3.0_07 September 2020
APPENDIX 1 TFLs Shells

 MC2 Therapeutics
 MC2-01-C6

Listing 16.2.9.10 Pharmacokinetic Concentrations
 All Enrolled subjects
 Page X of X

| Country/Site ID/ Subject ID | Age(Years) / | Analyte | Visit | Time Point | Date, Time of Sample/ Study Day/ Relative Time (hours) | Date, Time of Last Administration of Study Drug/ Study Day | Result | Reason if Not Done |
|-----------------------------------|-----------------|---|----------|--------------|--|---|--------|-----------------------|
| XXX/XX/XXXX | 14/F/A/NHL | Betamethasone 17P plasma concentration (pg/mL) | Scr V2 | | | | XX.X | |
| | | | V2/Week2 | Pre-Dose | YYYY-MM-DD HH:MM/ XX | YYYY-MM-DD HH:MM/ XX | XX.X | |
| | | | V3/Week4 | Pre-Dose | YYYY-MM-DD HH:MM/ XX (-X.XX) | YYYY-MM-DD HH:MM/ XX | XX.X | |
| | | | | 1h Post-Dose | YYYY-MM-DD HH:MM/ XX (X.XX) | YYYY-MM-DD HH:MM/ XX | XX.X | |
| | | | | 3h Post-Dose | YYYY-MM-DD HH:MM/ XX (X.XX) | YYYY-MM-DD HH:MM/ XX | XX.X | |
| | | | | 5h Post-Dose | YYYY-MM-DD HH:MM/ XX (X.XX) | YYYY-MM-DD HH:MM/ XX | XX.X | |
| | | | V5/Week8 | | YYYY-MM-DD HH:MM/ XX | YYYY-MM-DD HH:MM/ XX | XX.X | |
| | | BDP plasma concentration (pg/mL) | Scr V2 | | | | XX.X | |
| | | | V2/Week2 | Pre-Dose | YYYY-MM-DD HH:MM/ XX | YYYY-MM-DD HH:MM/ XX | XX.X | |
| | | | V3/Week4 | Pre-Dose | YYYY-MM-DD HH:MM/ XX (-X.XX) | YYYY-MM-DD HH:MM/ XX | XX.X | |
| | | | | 1h Post-Dose | YYYY-MM-DD HH:MM/ XX (X.XX) | YYYY-MM-DD HH:MM/ XX | XX.X | |
| | | | | 3h Post-Dose | YYYY-MM-DD HH:MM/ XX (X.XX) | YYYY-MM-DD HH:MM/ XX | XX.X | |
| | | | | 5h Post-Dose | YYYY-MM-DD HH:MM/ XX (X.XX) | YYYY-MM-DD HH:MM/ XX | XX.X | |
| | | | V5/Week8 | | YYYY-MM-DD HH:MM/ XX | YYYY-MM-DD HH:MM/ XX | XX.X | |
| | ... | ... | ... | ... | ... | ... | ... | |

Country: CZE=Czech Republic, HUN=Hungary, DEU=Germany; Sex: F=Female, M=Male;

Race: A=Asian, B=Black or African American, W=White, O=Other; Ethnicity: HL=Hispanic or Latino, NHL=Not Hispanic or Latino.

BDP=Betamethasone dipropionate; BLQ=Below Limit of Quantification.

Path to the program code, date and time of output/ Datasets used

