6.2 Dosing Regimen

Subjects are to apply the IP topically once daily, preferably in the evening, for 8 weeks. The subject should apply enough IP to treat the entire affected areas and rub in gently to ensure that the plaques are saturated with the medication. Up to 3 tubes of 60 gram will be dispensed for a treatment period of two weeks including the allowed visit window of 2 days.

The IP is applied to affected areas on the:

- scalp
- trunk (including the neck)
- limbs
 - arms (including the back of the hands)
 - legs (including the buttocks and the top of the feet).

Only affected areas are to be treated. The subjects should therefore not continue treatment on a skin area which has been cleared but treatment may be restarted in case of recurrence at the subjects discretion (Section 6.3).

The face, genitals, and intertriginous areas should not be treated with the IP. The first application is done at Day 0 under the supervision and instruction of the trial staff. Subsequent applications will be applied by the subject or by the parent(s) or legal guardian(s).

All subjects are instructed to apply IP in the morning on the day before the Week 2, Week 4 and Week 8 visits. On the day of these visits, the subjects should not apply any IP before the visit.

Subjects are to record the date and time of application in the subject dosing diary (with the assistance of the parent(s) or legal guardian(s), as needed). The treated area should not exceed 30% of the BSA.

In case an AE reported in one area of the body lead the investigator to the decision to discontinue treatment this will apply for treatment in general and not only to the area for which the AE was reported.

Detailed application instructions will be provided in the subject instructions.

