- **IP application and PK blood samples:** instruct the parent(s), legal guardian(s) or subjects to apply the IP in the morning on the day before the Week 2, Week 4 and Week 8 visits. On the day of these visits, the subjects should not apply any IP before the visit. A reminder to the parent(s), legal guardian(s) or subjects may be needed a few days before the scheduled visit. If the subject has applied the IP in the morning prior to the visit, the visit must be rescheduled.

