7.6.2 HPA axis suppression/ ACTH challenge test

Adrenal function will be assessed in a challenge test with an intravenous dose of ACTH (cosyntropin). Measurement of serum cortisol levels pre- and post- stimulation with cosyntropin 0.25 mg is the accepted standard method used to evaluate adrenal suppression. The ACTH challenge test will be performed at SV2, Week 4 and Week 8 visits. The test consists of blood sampling starting between 7 and 9 am. Following the blood sample, an intravenous bolus injection of 0.25 mg cosyntropin is given at time zero ($t=0$ minutes). Serum cortisol concentration at $t=30$ minutes will reflect stimulation of the adrenal glands induced by cosyntropin.

The following criterion will define an adrenal suppression:

- the 30-minute post-stimulation level below 18 $\mu\text{g}/\text{dL}$ (500 nmol/l).

Week 4: If HPA axis suppression is noted at Week 4, the application with the MC2-01 cream should be discontinued. The subject should continue in the trial and the ACTH challenge test is repeated at the Week 8 visit. If HPA axis suppression is noted at Week 8, the ACTH challenge test has to be repeated at a follow-up visit 28 days (\pm 2 days) after the Week 8 visit (see [Section 7.12](#)).

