**MC2-01-C6_STATISTICAL ANALYSIS PLAN_Final 3.0_07 September 2020**

IP before the visit. A reminder to the subject may be needed a few days before the scheduled visit.

The samples will be assayed for concentrations of the active ingredients (BDP and CAL) and for their major metabolites (betamethasone 17-propionate and MC180, respectively).

All available concentration results will be summarised by analyte and time point using appropriate descriptive statistics. Individual concentration versus time curves will be plotted (linear and semi-log plots) using actual time points.

Measured PK concentrations will be presented using standard descriptive statistics as described in section 7. Additionally, geometric mean and CV(%) will be presented.

Non-quantifiable (BLQ) levels of the analyte will be substituted by LLOQ for descriptive summaries and graphical presentation.

Plasma PK parameters at Week 4 (AUC_{0-t}, AUC₀₋₅, C_{max}, and T_{max}) will be calculated. The PK parameters AUC₀₋₅ and C_{max} will be calculated using standard formulas inserting the LLOQ for non-quantifiable levels of the analyte. For a given analyte, the PK parameters AUC_{0-t} and T_{max} will be calculated if at least one post-dose time-point shows a quantifiable level of the analyte. PK parameter values will be rounded to the precision of the raw data from which it was derived (C_{max}) or to 3 significant digits (AUC_{0-t}, AUC₀₋₅). T_{max} will be rounded to two decimal places.

Pharmacokinetic Parameters Derivations:

AUC_{0-t} (pg*h/mL): The area under the curve spanning time interval from 0 to t (up to the last time point with measurable concentration above the quantification limit) will be calculated using the linear trapezoidal rule based on actual relative time of sampling.

- 1) Actual relative time of each sample will be derived as the difference between the datetime value of the corresponding sample and the datetime value of drug application, in hours. The time of the pre-dose sample will be set to 0.
- 2) For the calculation of AUC_{0-t} BLQ values before the first reported measurable concentration (including pre-dose) will be substituted by LLOQ. The BLQ values after the last evaluable concentration will be set to missing.
- 3) Linear trapezoidal method is used. The area under the curve is defined as the sum of trapezoids across all pairs of time points from pre-dose to 5h post-dose at Visit 3 / Week 4.

Linear trapezoidal rule:

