APPENDIX 1 TFLs Shells

Pharmacokinetics Analyses

MC2 Therapeutics
MC2-01-C6Table 14.2.1.1 Individual and Summarized BDP Plasma Concentrations
PK population
Page X of X

| Subject Number/ Statistic | SV2 | Week 2 pre-dose | Week 4 pre-dose | 1h | 3h | 5h | Week 8 pre-dose |
|------------------------------|-------------|--------------------|--------------------|-------------|-------------|-------------|--------------------|
| XXXXXXXXXXXXXX | XX.XXX | XX.XXX | XX.XXX | XX.XXX | XX.XXX | XX.XXX | XX.XXX |
| XXXXXXXXXXXXXX | XX.XXX | XX.XXX | XX.XXX | XX.XXX | XX.XXX | XX.XXX | XX.XXX |
| XXXXXXXXXXXXXX | XX.XXX | XX.XXX | XX.XXX | XX.XXX | XX.XXX | XX.XXX | XX.XXX |
| XXXXXXXXXXXXXX | XX.XXX | XX.XXX | XX.XXX | XX.XXX | XX.XXX | XX.XXX | XX.XXX |
| ... | | | | | | | |
| XXXXXXXXXXXXXX | XX.XXX | XX.XXX | XX.XXX | XX.XXX | XX.XXX | XX.XXX | XX.XXX |
| n | XX | XX | XX | XX | XX | XX | XX |
| nquant | XX | XX | XX | XX | XX | XX | XX |
| Mean | XX.X | XX.X | XX.X | XX.X | XX.X | XX.X | XX.X |
| SD | XX.X | XX.X | XX.X | XX.X | XX.X | XX.X | XX.X |
| gMean | XX.X | XX.X | XX.X | XX.X | XX.X | XX.X | XX.X |
| gCV(%) | XX.X | XX.X | XX.X | XX.X | XX.X | XX.X | XX.X |
| Median | XX.X | XX.X | XX.X | XX.X | XX.X | XX.X | XX.X |
| Q1, Q3 | XX.X, XX.XX | XX.X, XX.XX | XX.X, XX.XX | XX.X, XX.XX | XX.X, XX.XX | XX.X, XX.XX | XX.X, XX.XX |
| Min, Max | XX.XX, XX.X | XX.XX, XX.X | XX.XX, XX.X | XX.XX, XX.X | XX.XX, XX.X | XX.XX, XX.X | XX.XX, XX.X |

BDP=Betamethasone dipropionate; BLQ=Below Limit of Quantification; gCV=Geometric Coefficient of Variation; gMean=Geometric Mean; LLOQ=Lower Limit of Quantification; PK=Pharmacokinetic.

BLQ concentrations were substituted with LLOQ for the calculation of summary statistics. LLOQ for BDP is XX.X pg/mL.

The unit of concentration is pg/mL.

n: the number of valid measurements; nquant: number of measurements with quantifiable level of analyte.

Path to the program code, date and time of output/ Datasets used/ Referenced Data Listings

Similar to table 14.2.1.1, the following tables will be constructed (with modification of underlined fragments):

MC2-01-C6_STATISTICAL ANALYSIS PLAN_Final 3.0_07 September 2020

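### Each pre-dose plasma summary ignores time since last application, so the Week 8 column can include subjects who stopped the cream weeks earlier

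*SAP*

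**What the plan says.** **Timing of application.** Protocol 6.2 sets the usual regimen: "Subjects are to apply the IP topically once daily, preferably in the evening, for 8 weeks". For PK visits it overrides that habit: "All subjects are instructed to apply IP in the morning on the day before the Week 2, Week 4 and Week 8 visits", with nothing applied on the visit day beforehand. The notes to Protocol Table 7-1 add a possible reminder and one enforcement rule: "If the subject has applied the IP in the morning prior to the visit, the visit must be rescheduled".

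**Stopping while staying in the trial.** Protocol 7.6.2 states: "If HPA axis suppression is noted at Week 4, the application with the MC2-01 cream should be discontinued"; the subject continues and is retested at Week 8. Protocol 6.3 lets a clear subject stop at the investigator's discretion, attend all visits, and restart at the subject's own discretion. Protocol 5.4 asks that anyone who discontinues treatment still attend Week 8 if possible.

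**Analysis.** SAP Section 10 states: "All available concentration results will be summarised by analyte and time point using appropriate descriptive statistics". After SV2, the columns of Table 14.2.1.1 are "Week 2 pre-dose | Week 4 pre-dose | 1h | 3h | 5h | Week 8 pre-dose", each with its own n, mean and geometric mean. BLQ values are set to LLOQ. The PK population (SAP 6.2) requires the Week 4 clinic application and one Week 4 draw; it sets no condition on the preceding application or on being on treatment at Week 8.

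**Data held.** Listing 16.2.9.10 prints sample time beside "Date, Time of Last Administration of Study Drug/ Study Day" for the Week 2, Week 4 and Week 8 samples. It derives a relative time only at Week 4, where it is measured from the clinic application.

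**The concern.** A column headed pre-dose suggests a level at the end of a dosing interval of about 24 hours in someone using the cream. The SAP does nothing to make that true. It has no acceptance window, flag, exclusion or split by time since last application; its visit windows (SAP Section 7) work on study day only.

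The stake is interpretation. Readers will naturally set the Week 2, Week 4 and Week 8 columns side by side to see whether systemic levels rise, hold or fall under continued maximal use. If some Week 8 values come from subjects off the cream for weeks, the Week 8 geometric mean is pulled down for a reason unrelated to absorption. The subjects stopped for HPA suppression are also those in whom exposure is of most interest.

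The SAP treats stopped treatment with more care elsewhere. Compliance excludes days of approved discontinuation (Section 9.1), and Week 8 HPA suppression is also shown by Week 4 suppression status (Section 9.5). The PK tables have no counterpart.

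**Working it through.** The plan states no figure to reproduce on this point. The check is interval arithmetic, followed by an illustration on assumed values.

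**1. Week 8 samples off treatment.** Visit windows are Day 28 ± 2, Day 42 ± 2 and Day 56 ± 2 (Protocol Table 7-1).
- Last application at Week 4: nominal 56 − 28 = 28 days; shortest (56 − 2) − (28 + 2) = 24; longest (56 + 2) − (28 − 2) = 32.
- Last application at Week 6 (clear): nominal 14 days; shortest 54 − 44 = 10; longest 58 − 40 = 18.

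The interval is shorter if the subject keeps applying cream until the Week 4 cortisol result arrives, or restarts after stopping when clear. Protocol 6.3 says dose modification occurs only after Week 4, yet allows stopping at any on-treatment visit. Those sentences need reconciling; only Weeks 4 and 6 are used here.

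**2. Samples on treatment.** Assumptions: sample at 07–09 h (the ACTH test window, as a proxy), morning application at 06–12 h, evening application at 18–22 h.

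| Last application | Shortest (h) | Longest (h) |
|---|---|---|
| Morning of the day before (instructed) | 24 + 7 − 12 = 19 | 24 + 9 − 6 = 27 |
| Evening before | 24 + 7 − 22 = 9 | 24 + 9 − 18 = 15 |
| Evening two days before | 48 + 7 − 22 = 33 | 48 + 9 − 18 = 39 |
| Morning two days before | 48 + 7 − 12 = 43 | 48 + 9 − 6 = 51 |

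The reschedule rule, as worded, addresses none of the last three rows.

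**3. Weight of one subject.** The interim follows completion by 7 treated subjects (SAP 6.1): 1/7 = 14% of a full column. At the PK target of 20, 1/20 = 5%.

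**4. Illustration, off-treatment Week 8 sample.** Suppose one of 7 subjects reads at LLOQ but on treatment would have read k times LLOQ. The geometric mean is multiplied by k^(−1/7). For assumed k = 1, 2 and 4 that is 1.00, 0.91 and 0.82: a fall of 0, 9 or 18%.

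**5. Illustration, shifted interval.** Assume single-exponential decline with half-life 6, 12 or 24 h.
- 12 h against 24 h: 2^(12/half-life) = 4.0, 2.0, 1.4. One such subject in 7 multiplies the geometric mean by ratio^(1/7) = 1.22, 1.10, 1.05.
- 48 h against 24 h: 2^(−24/half-life) = 0.06, 0.25, 0.5.

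If both values are BLQ, LLOQ substitution makes the effect zero.

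**6. Reach into the PK parameters.** Cmax uses values after dosing only (SAP Section 10). The Week 4 pre-dose value is the time-zero point of both AUCs. At nominal times 0, 1, 3 and 5 h its trapezoid weight is 0.5 × (1 − 0) = 0.5 h of 5 h, so doubling it in an otherwise flat profile raises AUC0-5 by 10%.

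**The case against.** The interval is controlled by design: a morning-before instruction, no application before the visit, a reminder, a reschedule rule and a dosing diary with date and time. All protocol deviations are listed, and the major ones are settled at the data review meeting. The secondary endpoints are AUC0-t, AUC0-5, Cmax and Tmax at Week 4; no trough or accumulation parameter and no comparison across visits is planned. Every concentration is printed by subject, and missed doses, stops, restarts and discontinuations are listed, so with 7 subjects a reader could trace any odd interval. The pre-dose wording at Week 8 follows the row name in Protocol Table 7-1.

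Much of this stands, and it rules out stronger readings that a reader might infer:

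- **That the three visits are pooled.** They are not. Each has its own column and statistics; the mixing is across subjects within a column.
- **That an evening-before application is accepted.** It contradicts the instruction. It simply triggers no stated action.
- **That mixed intervals have occurred.** Nothing in the documents shows a mistimed sample.
- **That the main statistics should be restricted to a window such as 20–28 h.** That would go against Protocol 8.7, which has all available concentrations summarised. On the clock times above it could also drop a compliant sample taken at 19 h.

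What the objection does not answer is Week 8. Off-treatment attendance there is a planned outcome, not a deviation, so following the documents exactly puts those samples into the Week 8 pre-dose statistics without a mark. Being able to trace them through several listings does not correct the summary.

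**Conclusion.** The concern holds in limited form. Each pre-dose column summarises subjects regardless of time since last application. At Week 8 the plan itself creates samples up to about 24 to 32 days after the last application and summarises them unflagged. Shifted intervals at Weeks 2, 4 and 8 through evening-before or missed applications are possible and unhandled, but not shown.

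The day counts assume that the last application was at the Week 4 visit and was not resumed. The percentage effects rest wholly on assumed half-lives or assumed multiples of LLOQ; the documents give neither, so the true size is unknown and may be nil where most values are BLQ. The output is descriptive and secondary. The primary endpoints and Cmax are untouched, and the AUCs are affected only through one lightly weighted point. The change is still worth making, because it costs little and removes a misleading reading.

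**What to change.** 1. Derive hours since last application as sample time minus last-administration time, both already in Listing 16.2.9.10. Print it for the Week 2, Week 4 pre-dose and Week 8 samples.
2. Flag samples from subjects off treatment, and samples outside a pre-stated window wide enough to cover the instructed morning-before interval.
3. In Tables 14.2.1.1 to 14.2.1.4, keep the planned all-sample summary. Add a second summary of these three columns without the flagged samples, with the number flagged, and mark those values in the individual rows.
4. Relabel the Week 8 column, for example as a single Week 8 sample, so that off-treatment values are not called pre-dose.

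The cost is one derived variable, one flag, extra summary rows and a footnote. The downside is a smaller n in the added summary. No dosing or visit rule changes. SAP Section 2 allows revision before the interim database lock; otherwise the change belongs in the separate SAP for the final analysis, should recruitment resume.
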